
Notes:
 
 Due to blood volume restrictions, some laboratory tests may not be collected. Laboratory samples are recommended to be collected as described in the sponsor provided weight-based prioritization chart. If ETV occurs on the same day as the scheduled visit, any assessments/procedures conducted during the scheduled visit should not be repeated for a separate ETV. The required post-treatment follow-up visits should occur for all study participants, except for those with concurrent infections (see Section 5.1.5 for details). 								
Visit No	V67	V68	V69	Early termination	Post-Treatment Follow-Up Period (PTFU)			Notes
				ETV	V801	V802	V803	V803 is an additional follow-up based on neutrophil count (Section 5.1.5).
Study Week	W256	W260	W264	Any Week	LV (or ETV) + 4W	LV (or ETV) + 8W	LV (or ETV) + 12W	
Study Days (Approximately)	1792 ± 7d	1820 ± 7d	1848 ± 7d	Any Day	± 7d	± 7d	± 7d	
Treatment Visits	X	X						Treatment visits are intended only for the dispensation and on-site administration of ixekizumab for the participants CCI [REDACTED] who have opted for on-site administration.
Inventory 2 Short Form (CDI-2)								
Pain Numeric Rating Scale			X	X				
Morning Joint Stiffness Duration			X	X				
Parent's Global Assessment of Well-Being			X	X				To be completed by caregiver until participant is >14 years of age, at which time, the participant will complete their own questionnaires.
Laboratory Tests								
Acute phase reactant (hsCRP)			X	X				
Acute phase reactant (ESR)			X	X				To be performed locally.
Administer TB test(s) (if applicable)	TB testing required only based on clinical assessment of TB risk and according to local regulations and/or local standard of care Section 9.4.6; Appendix 2).						QuantiFERON-TB Gold, T-Spot or PPD (if applicable) (Section 9.4.6; Appendix 2) PPD to be read locally.	
HBV DNA (if applicable)			X	X			X	Positive for HBcAb requires a follow up test for HBV DNA. See Section 9.4.4 for details.
Urine pregnancy test			X	X	X	X	X	See Section 9.4.5 and Appendix 6 for details. Females only. To be performed locally.
Clinical chemistry			X	X	X	X	X	
Hematology			X	X	X	X	X	


Notes:
 
 Due to blood volume restrictions, some laboratory tests may not be collected. Laboratory samples are recommended to be collected as described in the sponsor provided weight-based prioritization chart. If ETV occurs on the same day as the scheduled visit, any assessments/procedures conducted during the scheduled visit should not be repeated for a separate ETV. The required post-treatment follow-up visits should occur for all study participants, except for those with concurrent infections (see Section 5.1.5 for details). 								
Visit No	V67	V68	V69	Early termination	Post-Treatment Follow-Up Period (PTFU)			Notes
				ETV	V801	V802	V803	V803 is an additional follow-up based on neutrophil count (Section 5.1.5).
Study Week	W256	W260	W264	Any Week	LV (or ETV) + 4W	LV (or ETV) + 8W	LV (or ETV) + 12W	
Study Days (Approximately)	1792 ± 7d	1820 ± 7d	1848 ± 7d	Any Day	± 7d	± 7d	± 7d	
Treatment Visits	X	X						Treatment visits are intended only for the dispensation and on-site administration of ixekizumab for the participants CCI [REDACTED] [REDACTED] who have opted for on-site administration.
Urinalysis			X	X				
PK sample			X	X		X		At regular visits (i.e., when ixekizumab is administered on site to all the participants), PK samples should be collected prior to administration of ixekizumab.
Immunogenicity sample			X	X		X		See Section 9.6.1. All samples for immunogenicity should be taken predose when applicable and possible.

Abbreviations: AESI = adverse events of special interest; BP = blood pressure; d = days; DNA = deoxyribonucleic acid; EQ-5D-Y = European Quality of Life-5 Dimensions-Youth; ESR = erythrocyte sedimentation rate; ETV = Early Termination Visit; HBcAb = hepatitis B core antibody; HBV = hepatitis B virus; hsCRP = high-sensitivity C-reactive protein; IBD = inflammatory bowel disease; LEI = Leeds Enthesitis Index; LV = Last Visit; No = number; PK = pharmacokinetics; PPD = purified protein derivative; RNA = ribonucleic acid; TB = tuberculosis; V = study visit; W = study week.

Notes: If ETV occurs on the same day as the scheduled visit, any assessments/ procedures conducted during the scheduled visit should not be repeated for a separate ETV. Post-Treatment Follow-Up Period — This applies only to participants who do not enter the long-term extension study. Treatment Visits are intended for the dispensation and/or site administration of the study treatment. Because of blood volume restrictions, some laboratory tests may not be collected. Laboratory samples are recommended to be collected as described in the sponsor provided weight-based prioritization chart.

3. Introduction

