- CCI every 2 weeks (Q2W) CCI
- CCI Q2W CCI

Study RHCG will be conducted in 4 parts:

- Open-label treatment (OLT) Period: 16 weeks.
- OLE Period: 88 weeks.
- LTE Period: 160 weeks.
- Post-treatment follow-up (PTFU; Visits 801, 802, and 803): 4 to 12 weeks after the last visit.

Participants who complete the OLT period may continue to the OLE period of the study. Participants who complete the OLT and OLE periods of this study may participate in an open-label LTE period.

Participants receiving adalimumab during the OLT period who did NOT attain a JIA ACR 30 response at Week 16 will be switched to ixekizumab in the OLE period. Participants receiving adalimumab during the OLT period who did attain a JIA ACR 30 response at Week 16 will be given the option to switch or not to switch to ixekizumab in the OLE period. The decision to switch for participants who achieved a JIA ACR 30 response will be left to the participant/participant's caregiver and investigator. A switch from adalimumab to ixekizumab during the OLE period may also occur at any other visit after Week 16 based on the participant/participant's caregiver and investigator's decision. After switching to ixekizumab, the participants will not have the option to resume adalimumab treatment during the remainder of the trial participation. Any adalimumab participants that complete the open label extension period of the study will be reassigned to ixekizumab starting with Treatment Period 3 (refer to Section 6.1 for additional details). Adalimumab participants who choose not to switch to ixekizumab at the end of the open label period will enter the PTFU and be considered study completers.

Participant who do not enroll in the LTE study or discontinued early (participants who have received at least 1 dose of study drug) should enter the PTFU period and complete through Visit 802. Participants may be followed beyond Visit 802 for continued monitoring of their neutrophil counts if determined by the sponsor/investigator that additional monitoring is needed. If a participant discontinues study drug early, the participant will complete the early termination visit (ETV) and then enter the PTFU period.

Study Population:

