Hematology			X			X			X			X	
Urinalysis			X			X			X			X	
PK sample						X						X	At regular visits (i.e., when ixekizumab is administered on site to all the participants), PK samples should be collected prior to administration of ixekizumab.
Immunogenicity sample						X						X	See Section 9.6.1. All samples for immunogenicity should be taken predose when applicable and possible.

Abbreviations: AESI = adverse event of special interest; BP = blood pressure; d = days; EQ-5D-Y = European Quality of Life-5 Dimensions-

Youth; ESR = erythrocyte sedimentation rate; HBcAb = hepatitis B core antibody; HBV = hepatitis B virus; hsCRP = high-sensitivity C-reactive protein; IBD = inflammatory bowel disease; LEI = Leeds Enthesitis Index; No = number; PK = pharmacokinetics; PPD = purified protein derivative; TB = tuberculosis; V = study visit; W = study week.

Table RHCG.2.6. Schedule of Activities – Long Term Extension Period (V67 through V69)

Notes:								

 • Due to blood volume restrictions, some laboratory tests may not be collected. Laboratory samples are recommended to be collected as described in the sponsor provided weight-based prioritization chart. • If ETV occurs on the same day as the scheduled visit, any assessments/procedures conducted during the scheduled visit should not be repeated for a separate ETV. • The required post-treatment follow-up visits should occur for all study participants, except for those with concurrent infections (see Section 5.1.5 for details). 								
Visit No	V67	V68	V69	Early termination	Post-Treatment Follow-Up Period (PTFU)			Notes
				ETV	V801	V802	V803	V803 is an additional follow-up based on neutrophil count (Section 5.1.5).
Study Week	W256	W260	W264	Any Week	LV (or ETV) + 4W	LV (or ETV) + 8W	LV (or ETV) + 12W	
Study Days (Approximately)	1792 ± 7d	1820 ± 7d	1848 ± 7d	Any Day	± 7d	± 7d	± 7d	
Treatment Visits	X	X						Treatment visits are intended only for the dispensation and on-site administration of ixekizumab for the participants CCI [REDACTED] who have opted for on-site administration.
Immunization record			X	X				Immunizations occurred during the participation in the study.
Physical examination			X	X				Excluding pelvic, rectal, and breast examinations.
Height			X	X				

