Participants who complete the OLT and OLE are eligible to enter the LTE part of the study period. All participants entering the LTE portion of the study period will receive weight-based ixekizumab at Week 104. Participants who were previously assigned to adalimumab will be switched to ixekizumab as described in Section 7.1 Treatments Administered. If a participant previously assigned to adalimumab does not want to switch to ixekizumab in the LTE period of the study, the patient should initiate the early termination visit (ETV) process at Week 104. These participants will be considered to have completed the study. Participants who have completed PTFU will have completed the study. Participants who have received at least 1 dose of study drug and who discontinued early (patients who have received at least 1 dose of study drug) should enter the PTFU period and complete through Visit 802. Participants may be followed beyond Visit 802 for continued monitoring of their neutrophil counts or because of any other

safety concerns if determined by the sponsor/investigator that additional monitoring is needed. If a participant discontinues study drug early, the participant will complete the ETV and then enter the PTFU period.

Interim analyses are described in Section 10.3.8. An interim analysis will be performed to determine if the study should be stopped for futility when 40 ixekizumab--treated participants have completed 16 weeks of treatment.

[figure not shown]
The study will enroll at least 100 participants with JIA categories of ERA or JPsA. Among participants who are bDMARD-naïve, at least 20 participants will be randomized to ixekizumab and at least 20 participants will be randomized to adalimumab.

Randomization will be stratified based on the subset of JIA (ERA or JPsA).

The remaining participants (approximately 60 participants) who are either bDMARD-naïve or bDMARD-IR will be assigned to ixekizumab.

The LTE period will include the following on-site visits:

- Regular visits (every 12 weeks, with the exception of Visits 30 and 31/Weeks 108 and 112): both for participants CCI [REDACTED]
 - During regular visits, ixekizumab will be administered on site to all participants (regardless of their weight).
- Treatment visits (every 4 to 8 weeks starting with Visit 32/Week 116): for participants CCI [REDACTED] (and those participants CCI [REDACTED] who have opted to receive ixekizumab on site).

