5.1.5. Post-Treatment Follow-Up Period

Participants who have received at least 1 dose of study drug (including those who do not enter in the LTE period or discontinued early) should enter the PTFU period for a minimum of 12 weeks after their last regularly scheduled visits (or the date of their ETV). Required study visits should occur at 4 weeks after and at 8 weeks after the last regularly scheduled visit (or the date of the participant's ETV) (Visits 801 and 802, respectively), except for participants with concurrent infections that require systemic anti-infective therapy (described below).

If, at the last scheduled visit or ETV, a participant's neutrophil count is <1500 cells/ μ L ($<1.50 \times 10^3/\mu\text{L}$ or <1.50 GI/L) and less than the participant's baseline neutrophil count, the following measures should be taken:

- Participants with concurrent infection: If there is a concurrent infection that requires systemic anti-infective therapy, the participant should receive appropriate medical care and a repeat test for neutrophil count should be performed at least Q4W (or sooner as appropriate) until resolution of infection. Upon resolution of infection, the neutrophil count should be monitored using the required study visits in the PTFU period design at Visits 801 (4 weeks after resolution of infection), 802 (8 weeks after last visit), and 803 (if necessary; 12 weeks after last visit); additional visits may be required depending on the degree of neutropenia.
- Participants without concurrent infection: If there is no concurrent infection that requires systemic anti-infective therapy, the neutrophil count should be monitored using the required study visits in the PTFU period design, Visits 801 (4 weeks post ETV or last regularly scheduled visit), 802, and 803 (if necessary); additional visits may be required depending on the degree of neutropenia.
- For Visit 801 and subsequent visits, the following monitoring applies:
 - As long as a participant's neutrophil count is <1000 cells/ μ L ($<1.00 \times 10^3/\mu\text{L}$ or <1.00 GI/L) at any follow-up visit, the participant should return for additional visits at least Q4W (unscheduled visits may be required).

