5.3. End of Study Definition

A participant is considered to have completed the study if he/she has completed all required phases of the study including the last visit or the last scheduled procedure shown in the Schedule of Activities (Section 2). Participants on adalimumab completing Visit 29/Week 104 are considered to have completed the study treatment if they do not wish to continue on ixekizumab.

The end of the study is defined as the date of the last visit of the last participant in the study or last scheduled procedure shown in the SoA for the last participant in the trial globally.

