- **Post-Treatment Follow-Up Period** (PTFU) is for safety monitoring after treatment discontinuation for any subject receiving at least 1 dose of study drug. Participants who have received at least 1 dose of study drug should enter the PTFU period for a minimum of 12 weeks after the last treatment period visit (Week 104) or ETV their last regularly scheduled visits (or the date of their ETV).

Figure RHCG.5.1 illustrates the study design for the main protocol.

Abbreviations: ACR = American College of Rheumatology; bDMARD = biologic disease-modifying antirheumatic drug; bDMARD-IR = inadequate response to biologic disease-modifying antirheumatic drug; ERA = enthesitis-related arthritis; ETV = early termination visit; JIA = juvenile idiopathic arthritis; JPsA = Juvenile Psoriatic Arthritis; LV = last visit; OLE = open-label extension; PTFU = post-treatment follow-up period; OLT = open-label treatment; Q2W = every other week; Q4W = every 4 weeks; TV = treatment visit; Tx = treatment x; V = visit; W = week.

- a Patients who are bDMARD-naïve will be randomized to ixekizumab or adalimumab in a 1:1 ratio. At least 20 patients will be randomized to ixekizumab and 20 patients to adalimumab. Randomization will be stratified based on the category of JIA (ERA or JPsA). The remaining patients (approximately 60 patients) who are bDMARD-naïve or bDMARD-IR will be assigned to ixekizumab.
- b Patients receiving adalimumab during the OLT period who did NOT attain a JIA ACR30 response at Week 16 will be switched to ixekizumab in the OLE period. Patients receiving adalimumab during the OLT period who did attain a JIA ACR30 response at Week 16 will be given the option to switch or not to switch to ixekizumab in the OLE period.
- c Regular visits will occur every 3 months, but patients will have monthly treatment visits to the site primarily for injection purposes. Participants who are treated with adalimumab through Week 104 may decide not to switch to ixekizumab at Week 104 and enter the PTFU period.

Figure RHCG.5.1. Illustration of study design for Study I1F-MC-RHCG.

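### The closing note of the Schedule of Activities limits post-treatment follow-up to participants who do not enter the long-term extension, contrary to the schedule table, Section 5.1.5 and SAP 5.1; an LTE completer would lose V801 and V802

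*Protocol*

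**What the plan says.** The closing note stands at the end of Section 2, after Table RHCG.2.6, the only schedule table with columns for V801 to V803. On the PTFU it says: "This applies only to participants who do not enter the long-term extension study".

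Three places say otherwise:
- The notes to Table RHCG.2.6 state: "The required post-treatment follow-up visits should occur for all study participants, except for those with concurrent infections". The exception points to Section 5.1.5, where a concurrent infection changes the timing of the visits.
- Section 5.1.5 assigns to the PTFU "Participants who have received at least 1 dose of study drug (including those who do not enter in the LTE period or discontinued early". Non-entrants to the LTE are there only as an included subset.
- SAP 5.1 describes the period as "for safety monitoring after treatment discontinuation for any subject receiving at least 1 dose of study drug".

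Two sentences are narrower. The synopsis names "Participant who do not enroll in the LTE study or discontinued early". Section 5.1 says that dosed participants who discontinued early "should enter the PTFU period and complete through Visit 802". Neither names LTE completers.

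On duration, Section 5.1.5 requires visits 4 and 8 weeks after the last visit. It and SAP 5.1 also state a 12-week minimum for the period.

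On analysis, SAP 6.12 takes the PTFU baseline at or before Week 104 or the early termination visit (ETV). SAP 6.12.2.1 uses the same point for the start and baseline severity of follow-up-emergent adverse events.

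**The concern.** The note and the table above it cannot both be followed for someone who enters the LTE. The conflict sits in the part of the protocol that other sections rely on: the study-completion definition (5.3), follow-up after stopping drug (8.1.1) and the end of SAE collection (9.2.2) all refer to the Schedule.

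At stake are the off-drug safety data of children finishing up to five years of treatment. The V801 and V802 assessments are adverse events, concomitant medication, chemistry, haematology (including neutrophil recovery) and pregnancy tests, with PK and antibody samples at V802. V802 also falls at the end of the 12-week contraception period after the last ixekizumab dose in Section 6.1. A missed visit cannot be recovered once a participant has been closed out.

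The SAP anchors are a second, related defect. They fit a study that ends treatment at Week 104, but LTE completers enter the PTFU after Week 264.

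**Working it through.** **Who enters the PTFU, by source**

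| Source | LTE completers | Stop during the LTE | Do not enter the LTE |
|---|---|---|---|
| Schedule, closing note | no | no, read literally | yes |
| Table RHCG.2.6 notes | yes | yes | yes |
| Section 5.1.5 | yes | yes | yes |
| SAP 5.1 | yes | yes | yes |
| Synopsis | not named | yes | yes |
| Section 5.1 | not named | yes | adalimumab non-switchers, in the figure footnote |

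Only the closing note excludes LTE completers. The synopsis and Section 5.1 are silent on them.

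**Calendar check**

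1. The study days in Table RHCG.2.6 reproduce as 7 × week: 7 × 256 = 1792 (V67), 7 × 260 = 1820 (V68), 7 × 264 = 1848 (V69). All three match.
2. Last scheduled dose: the table marks administration at V67 and V68 and none at V69, so the last dose is at Week 260. Protocol 10.3.1.3 agrees once its transposed labels (Week 68, Visit 260) are put right. SAP 6.1.2.3 instead places an injection at Week 264, so both cases are shown.
3. PTFU visits are the last visit (Week 264) plus 4, 8 and, if needed, 12 weeks.

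| Visit | Week | Weeks after a Week 260 dose | Weeks after a Week 264 dose |
|---|---|---|---|
| V69 (end of observation under the note) | 264 | 264 − 260 = 4 | 0 |
| V801 (required) | 264 + 4 = 268 | 8 | 4 |
| V802 (required) | 264 + 8 = 272 | 12 | 8 |
| V803 (if needed) | 264 + 12 = 276 | 16 | 12 |

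4. Loss under the note: 272 − 264 = 8 weeks and 2 of 2 required visits. The loss is the same whichever last dose is used.
5. The 12-week minimum in Section 5.1.5 and SAP 5.1 would run to Week 276. Only V801 and V802 are required, so the loss is counted to Week 272.

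**SAP anchors**

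For an LTE completer, Week 104 lies 264 − 104 = 160 weeks before the last treatment visit. The SAP 6.12 baseline conflicts with the last sentence of Protocol 10.3.1.4, which takes the last value before PTFU entry. It also conflicts with the main wording of SAP 6.1.2.4, where Week 104 appears only as an outdated explanatory phrase. SAP 6.12.3.2 (follow-up-emergent SAEs) and 6.12.4.2 (neutrophils) already use the last treatment-period visit or the visit before PTFU entry.

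**The case against.** The best reply is that this is an editorial slip. The note repeats ETV and blood-volume remarks already at the head of Table RHCG.2.6, and it speaks of an extension study although Section 7.8.1 makes the LTE part of this one. It would be correct beneath the table ending at Week 104, so it may be leftover or displaced text. The all-participants note is repeated through the pages of Table RHCG.2.6, the grid shows V801 to V803 after V69, and Appendix 7 budgets blood for them beside the LTE visits. A careful site would hold the visits.

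Most of this stands. It shows which reading is intended, and it rules out a stronger inference that the sponsor planned to omit follow-up after the LTE. It does not remove the contradiction: the note is current text, and it governs the only PTFU columns.

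Other inferences go too far:
- A reader might conclude that participants who stop during the LTE also lose follow-up. The note alone says so, but the synopsis, Section 5.1 and Section 5.1.5 expressly send them to the PTFU.
- The hepatitis B DNA test should not be counted as lost. Section 9.4.11.2 independently requires it 12 weeks after the last dose, and the grid marks its PTFU sample at V803. Pregnancy testing at PTFU visits is also restated in Section 9.4.5.
- The SAP anchors need not inflate counts through double counting. SAP 6.12.2.1 does not count an event as follow-up emergent if it was already counted as treatment emergent.

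**Conclusion.** The closing note is wrong as written and should be corrected. Followed literally, it ends observation of an LTE completer 4 weeks after the last scheduled dose instead of at least 12, losing 8 weeks and both required visits. This assumes a last dose at Week 260 and PTFU visits on schedule. V69 still provides one set of safety, PK and antibody data. The risk is mainly to LTE completers at sites that follow the note, and the documents give no figure for how many that would be.

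The Week 104 anchors in SAP 6.12 and 6.12.2.1 are a separate error for the same participants. They affect descriptive safety summaries only. Neither defect touches the Week 16 endpoint or the decision rule.

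**What to change.** - **Schedule of Activities:** delete the note, or replace it with: *All participants who received at least 1 dose enter the PTFU after V69, after an ETV at any time, or after Week 104 if not entering the LTE.*
- **Synopsis and Section 5.1:** add LTE completers to the PTFU sentences.
- **SAP 6.12 and 6.12.2.1:** anchor the PTFU baseline, and the start and baseline severity of follow-up-emergent adverse events, to the last treatment-period visit (V69, ETV, or Week 104 if not entering the LTE).
- **Protocol 10.3.1.4, SAP 5.1 and SAP 6.1.2.4:** remove the outdated Week 104 wording.
- **Section 5.1.5 and SAP 5.1:** reconcile the 12-week minimum with the two required visits, which end at 8 weeks.

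The cost is wording edits in the next protocol and SAP amendment, with whatever ethics review that amendment needs under Appendix 3, and a memo to sites. No visit or procedure is added, because V801 to V803 are already in Table RHCG.2.6.
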